TITLE: Evaluation of Abdominal Wall Block with Liposomal Bupivacaine for Post-Operative Analgesia in Donor Nephrectomy

NCT#: NCT03294109

DATE: May 20, 2020

Study Title:

“Evaluation of Abdominal Wall Block with Liposomal Bupivacaine for Post-Operative Analgesia in Donor Nephrectomy”

List of Abbreviations:

TAP block: Transverse abdominis plane block

TQL block: Transmuscular quadratus lumborum block

LA: Local Anesthetic

Principal Investigator, Research Team, and Study Site:

Principal investigators: [name] MD, [name] MD

Co-Investigators: [name] MD, [name] MD, [name] MD, [name] MD, [name], [name], [name]

Research team and contact information:

UCLA Department of Anesthesiology
and Perioperative Medicine

Ronald Reagan UCLA Medical Center

[name]

[name]

[contact]

University of California, Los Angeles

Department of Urology

David Geffen School of Medicine at UCLA

[name]

[name]

[name]

[contact]

Study site: UCLA Medical Center, Ronald Reagan Hospital

Background and study population

The study population will include patients greater than 18 years of age undergoing laparoscopic donor nephrectomy surgery.

Study Design

Randomized blinded controlled clinical trial

Sample Size

50 each arm. 100 total.

Study Duration

18-24 months.

Primary Objective

To determine the degree of pain control in patients receiving a long acting TQL block in addition to a short half-life TAP block compared to TAP block alone (i.e., the current standard of care) after laparoscopic donor nephrectomy. This outcome will be measured using pain scores on a numeric scale obtained during standard inpatient care as well as via the APS-POQR and PROMIS-29, two standard, validated questionnaires.

Secondary Objectives

- To determine patient satisfaction as measured by a satisfaction item at post-operative days 1 and 90.
- To measure changes in quality of life via the PROMIS-29, bowel function via the Bowel Habits Questionnaire (BHQ), male (International Index of Sexual Function; IISF) and female sexual function (Female Sexual Function Index; FSFI) across time and in the study group (patients receiving liposomal bupivacaine TQL block in addition to TAP block) as compared to our conventional post-operative pain management. See attached questionnaire schedule for timing of these items.

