- To determine if patient-reported nausea and vomiting at post-operative days 1, 3, 5, 10, and 30 is significantly decreased in patients in the study group.
- To measure the rate of block-related complications in the study group. Potential complications include local anesthetic toxicity, intravascular injection, persistent weakness or paresthesia, nerve injury, voiding dysfunction, persistent numbness, altered sexual function, bleeding/hematoma, hypotension, infection at the injection site, or other complaints related to the block.
- To determine if narcotic requirements postoperatively are lower in the study group. To determine total anesthetic and operative time, as well as costs.

Background and Significance:

Living kidney donors are carefully screened prior to recommending kidney donation. They are informed of the risks of surgery and the option of changing their mind until the day of kidney donation. All of the patients have an abdominal and pelvic CT scan to evaluate the renal anatomy and to screen for abnormalities. Our goal is to make the operation as minimally invasive as possible and to facilitate the return to normal function as quickly as possible. Currently, most patients need narcotics to control the pain after surgery. These medications can have significant side effects including nausea and constipation, which can delay recovery from the operation.

Since the first successful living donor kidney transplant between identical twins, the special nature of this operation and the anesthetic management has been debated (1). Extensive efforts have been made to improve the safety and reduce the morbidity of kidney donation. At UCLA, laparoscopic kidney donation was introduced in 1999, and is now the standard of care for approximately 150 of these operations annually. Ketorolac analgesia was added to reduce pain in 2002 and the procedure has continued to evolve to promote return to normal function as soon as possible (2). The median length of stay for these patients is currently 1.4 days.

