A review of the literature identified three publications with enhanced recovery from surgery (ERAS) protocols. The Univ. of Michigan protocol uses a transversus abdominus plane (TAP) block under ultrasound guidance using a hydrodissection technique with normal saline followed by 15 to 20 mL of 0.5% ropivacaine per side with length of stay (LOS) of 1 day after surgery (3). The Duke protocol uses a liposomal bupivacaine TAP block and a hand assisted approach, which also achieved a one day LOS (4). A randomized study of hand assisted laparoscopic kidney donation at the Univ. of Minnesota compared bupivacaine to liposomal bupivacaine for subcostal TAP block which showed a significant reduction in pain scores for the liposomal bupivacaine 24-48 hours after surgery, but a LOS of 2-3 days in both groups (5).

An alternative local anesthetic approach in laparoscopic gynecologic operations and pediatric pyeloplasty is the transmuscular quadratus lumborum (TQL) block. The most important advantage of TQL block over TAP block is a consistent posterior spread of local anesthetic up to the paravertebral space (6). In preliminary studies, we have placed a TQL block in 6 patients using bupivacaine and methylene blue. These patients had excellent pain relief for approximately 12 – 18 hours, but then had more need for outpatient narcotics after the local anesthetic effect wore off. In patients with bupivacaine TAP block, placed either by ultrasound, or by direct visualization with the laparoscope, pain relief is achieved for the anterior abdominal wall, but patients still need narcotics for relief of pain toward the back. Complications that have been reported with TQL block include hypotension which may have been due to sympathetic blockade, and motor dysfunction of the leg for over 24 hours (7,8). Based on our minimal experience with TQL block and review of the literature, it is our hypothesis that the optimal pain management for fully laparoscopic donor nephrectomy is a combined TQL block placed after the induction of anesthesia and a TAP block placed after the midline incision is closed using a long acting local anesthetic.

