Secondary objectives include patient satisfaction scores obtained with a validated satisfaction survey administered to each patient prior to discharge; nausea and vomiting requiring medical intervention; block-related complications noted in the immediate perioperative period or post-operative period; and total opiate requirement during the hospital stay and for 90 days after surgery. We will also monitor the return of bowel function, sexual function and general health using standardized quality of life instruments. Sexual function following kidney donation has not been closely evaluated; yet many patients ask about the potential impact of surgery on this bodily function that is important to a normal quality of life. Each patient will complete the validated survey instruments prior to and after kidney donation. Patients are not required to answer any questions. We will evaluate attitudes toward living kidney donation in relationship to pain control.

Study design/methodology:

This is a randomized, single-blinded controlled trial in patients greater than 18 years of age who have agreed to proceed with laparoscopic donor nephrectomy. Patients meeting these criteria will be offered participation in the study. They will be advised of the risks and potential benefits of the study. They will be advised of the request to answer surveys and have information regarding their care collected for research. They will be advised that participation requires the ability to answer questions using electronic communications. Participation is optional and standard anesthesia and pain control will be provided to all patients. Patients have the option to withdraw

from the study at any time and are not required to answer any of the survey questions. Enrolled patients will not know which treatment is provided.

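### The complication objective is stated for the study group alone, so for events that controls can also have it cannot show what the TQL block adds

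*Combined protocol and SAP*

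**What the plan says.** The protocol's Secondary Objectives list gives the safety aim as "To measure the rate of block-related complications in the study group". The potential complications that follow include "voiding dysfunction, persistent numbness, altered sexual function, bleeding/hematoma, hypotension, infection at the injection site".

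The neighbouring items in the list are comparative:
- Quality of life, bowel function and sexual function are assessed "as compared to our conventional post-operative pain management".
- The nausea and vomiting objective asks whether it "is significantly decreased in patients in the study group".
- The opioid objective reads "To determine if narcotic requirements postoperatively are lower in the study group".

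The Objectives section restates the safety outcome as "block-related complications noted in the immediate perioperative period or post-operative period". That wording is not confined to one arm, but it names no comparison.

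The Statistical Analysis Plan section gives t-tests for pain, nausea, 24-hour opiate use and satisfaction, and nothing for complications. It is silent on some other secondary outcomes too, so the main evidence here is the wording of the objective. The Study design/methodology section has complications charted in the electronic record, without restriction to one arm. It also describes randomization and a superficial sham needle insertion for controls.

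**The concern.** Controls undergo the same general anesthesia and nephrectomy, and receive the same bupivacaine TAP block and incision infiltration. Several listed events can therefore happen without a TQL block. A study-group rate for such an event mixes what the TQL block causes with what would have happened anyway, and cannot separate the two.

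Hypotension is the clearest example. The Background and Significance section says "Complications that have been reported with TQL block include hypotension which may have been due to sympathetic blockade", yet the block is placed soon after induction, when anesthesia itself can lower blood pressure.

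The protocol aims to judge benefit against cost of adding the block in carefully screened living donors. That judgment needs the harm the block adds. If the result were reported as the objective states, a reader would see how often donors with the block had an event, but not whether this exceeded the frequency without it.

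**Working it through.** **No planned figure to reproduce.** The documents give no complication rate and no complication sample size. Table 1 concerns pain scores and does not bear on this point.

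**Inputs from the documents.** There are 50 patients per arm (Sample Size). Both arms receive 20 mL plus 10 mL of 0.25% bupivacaine (Study design/methodology). At 2.5 mg/mL this is (20 + 10) × 2.5 = 75 mg.

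**Which events are affected.**
- Possible in both arms: hypotension, bleeding or hematoma, voiding dysfunction, persistent numbness.
- Tied to the TQL injection: intravascular injection at the TQL site, for example. The control needle passes only through the skin, so a study-group rate is a sensible description.
- Already compared elsewhere: sexual function, through the questionnaire objective.

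**Assumed inputs.** All event counts below are assumptions, varied over a range.

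**One-arm result.** For 15/50 = 30%, the exact (Clopper-Pearson) 95% CI is 17.9% to 44.6%. It is the same whatever happens in controls.

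**Two-arm result.** Wilson limits for each arm, with z = 1.96:

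(p + z²/2n ± z√[p(1−p)/n + z²/4n²]) / (1 + z²/n)

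The Newcombe interval for d = p₁ − p₂, where arm 1 is the study group and l and u are the Wilson limits:

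- lower = d − √[(p₁ − l₁)² + (u₂ − p₂)²]
- upper = d + √[(u₁ − p₁)² + (p₂ − l₂)²]

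For 15/50 the Wilson limits are 0.1910 and 0.4375. For 0/50 they are 0 and 0.0713.

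- 15 v 0, lower: 0.30 − √(0.1090² + 0.0713²) = 0.170.
- 15 v 0, upper: 0.30 + √(0.1375² + 0²) = 0.438.
- 15 v 15: 0 ± √(0.1090² + 0.1375²) = ±0.175.

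The same study-group result against four control counts:

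| Study group | Control | Excess, points (95% CI) |
|---|---|---|
| 15/50 | 0/50 | +30.0 (17.0 to 43.8) |
| 15/50 | 5/50 | +20.0 (4.3 to 34.9) |
| 15/50 | 10/50 | +10.0 (−7.0 to 26.3) |
| 15/50 | 15/50 | 0 (−17.5 to 17.5) |

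One study-group figure thus fits anything from no excess to 30 points. At a lower assumed count, 10/50 fits +20.0 (8.7 to 33.0) with 0/50 controls and 0 (−15.7 to 15.7) with 10/50.

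**Precision if both arms are reported.** With equal rates the interval is ±12.7 points at 10%, ±15.7 at 20%, ±17.5 at 30% and ±18.9 at 50%. For a rare event, 2/50 v 0/50 gives 4.0 points (−3.7 to 13.5).

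**The case against.** The strongest reply is that the concern hangs on one phrase. The restatement in the Objectives section is arm-neutral. So are the charting of complications, the review of major complications (Informed Consent Process) and the intermittent adverse-outcome analysis (Data Safety Monitoring). In a randomized trial, tabulating complications by arm is a natural reading. This softens the point, but none of these places states a comparison, and the only wording that names a group names one arm.

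A second reply is that the objective concerns block-related events, so attribution already removes the background. This stands for events tied to the injection. For the four shared events it does not. Case-by-case attribution cannot establish an excess, and only patients are stated to be blinded: "Enrolled patients will not know which treatment is provided".

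A third reply is that 50 per arm is too few. That is right for a test. With a normal approximation and two-sided alpha of 0.05 (assumed), 80% power needs about 33% v 10% or 47% v 20%, gaps of 23 and 27 points. It is a reason to report descriptively, not to omit the comparison.

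A reader might infer three stronger things that are not supported:

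- **That control complications will go unrecorded.** The charting text covers the study patients without regard to arm, so control data probably will exist.
- **That hypotension in the operating room will be missed.** The plan gives no definition and does not name the anesthesia record as a source. However, the restated outcome covers the immediate perioperative period and nothing excludes that record. Under-capture is not shown.
- **That reporting by arm would reliably detect an excess of 10 to 20 points.** The smallest observed differences whose Newcombe interval excludes zero are 5 v 0, 13 v 5, 19 v 10 and 25 v 15 out of 50, or 10 to 20 points. These are observed differences, not true excesses the trial would detect reliably. Fisher's exact p at those counts is 0.056, 0.066, 0.077 and 0.066.

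**Conclusion.** The concern holds, limited to listed events that controls can also have. For hypotension, bleeding or hematoma, voiding dysfunction and persistent numbness, the measure as stated cannot show the excess due to the TQL block, although the randomized sham control could supply the comparison. The gap is a missing stated comparison, not missing control data.

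The logic does not depend on any particular rate; the illustrative intervals do, and every count in them is assumed. Because the sham is only a skin puncture, the contrast would measure the whole TQL procedure together with the drug.

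Severity is minor. The outcome is secondary and descriptive, and the primary result, sample size and clinical care are unaffected. The case for acting is that the improvement is cheap.

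**What to change.** In Secondary Objectives, change *in the study group* to *in each group* for the complication item. Count the shared listed events in both arms whether or not staff attribute them to the block. An attributed, block-related count may be kept alongside.

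In the Statistical Analysis Plan section, add: *Each complication will be reported by arm as n/N with a risk difference and Newcombe 95% confidence interval, descriptively and without a hypothesis test. Events tied to the TQL injection, such as intravascular injection, may be reported as study-group rates with an exact 95% confidence interval.*

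The cost is a wording change and a short addition to the analysis plan, using data that would probably be charted anyway. There are three downsides:

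- With 50 per arm the intervals are wide, so small or moderate excesses stay unresolved.
- All-cause rates will look higher than a block-related count, because they include events from anesthesia and surgery.
- Charting by staff who are not stated to be blinded could bias the comparison, which should be noted when it is reported.

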Those patients who agree to participate and provide written consent will be enrolled into the study and instructed in the electronic completion of study questionnaires using the Urology Patient Data Waystation (UPDW). Unique, personalized log-in information will be sent to the patient either by email or using the secure MyChart messaging system, based on patient preference, to access UPDW for each time point. Initial questionnaires at enrollment will collect baseline quality of life, bowel and sexual function, and demographic data. When the surgery date has been determined, patients will receive a message to complete a second set of baseline survey questionnaires using the same system if their surgery date is more than 6 months past the date of completion of their initial baseline survey. Those participants who completed their initial baseline within 6 months of their surgery date will only complete one baseline survey.

When surgery is scheduled, each enrolled patient will be randomized (alternating, blocked randomization) to either the study group to receive liposomal bupivacaine TQL block in addition to standard of care post-operative pain management or to the control group to receive our current standard of care. Randomization will maintain equal numbers of participants in each group by sex due to the increased risk of post anesthesia nausea in females.

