The following study variables will be collected postoperatively following arrival in the post-anesthesia care unit: Current and maximum intensity pain scores will be documented by nurses in the electronic medical record (EMR). Total opiate dose consumed every 24 hours will be collected from EMR and electronic survey after discharge. Patient satisfaction will be evaluated using the Revised American Pain Society Patient Outcome Questionnaire (APS-POQ-R) provided on post-operative day 1 by a research assistant or study coordinator. The incidence of nausea or vomiting will be extracted from nursing notes and queried via electronic surveys. Post-discharge, which is typically 1-2 days following surgery, patients will be sent surveys delivered by the UPDW database server 3, 5, 10, 30, and 90 days post-surgery. If patients do not respond 90 days post-surgery study team will contact patients to attempt to have the exit survey completed.

Complications will be documented in the EMR by the anesthesia pain service, urology service, and nurses who will monitor these patients while admitted. Urology and study staff will follow the patients following discharge, including a post-operative office follow-up approximately 1 week post-surgery, as is standard of care

Study Population:

Patients at least 18 years of age undergoing laparoscopic donor nephrectomy. Pregnant patients will be excluded. Patients with local infection at the potential block site or any contraindication to kidney donation, local, or general anesthesia will be excluded.

Study Duration/Study Timeline:

We anticipate a high level of enrollment since most patients have previously consented to having a block placed and pain minimization is generally a high priority. Given the current volume of donor nephrectomies we expect enrollment to be complete within one year. The duration of the study will depend on the timing from consent for surgery until the operation is scheduled. In most cases this occurs within 2-3 months. The study data collections will conclude 90 days after surgery unless the patient was not able to complete the survey. Additional attempt to contact the patient after 90 days post-surgery may be enacted to have the patient(s) complete an exit survey. See the attached study time line in Appendix A.

Statistical Analysis Plan:

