Qualified participants will be identified by the donor nephrectomy surgeon using the EMR's schedule report for each clinic day (typically every Friday). All patients must consent to laparoscopic kidney donation prior to recruitment. Patients will be introduced to the study by the donor nephrectomy surgeon after the surgical consultation and tentative approval for kidney donation by the living donor team. At this time, the surgeon will discuss the differences between study arms, potential risks of the procedure, and any questions the patient asks.

If the patient is interested in participating, the surgeon will introduce the study coordinator or trained research assistant to inform the patient about the nature of the study, requirement to have access to electronic equipment to complete surveys, and requirement of sufficient ability to understand the questions in the English language given the personal nature of the some of the questions including bowel and sexual function. If the patient then wishes to participate, they will be guided through the informed consent document and given time to ask any questions by the study coordinator or trained research assistant. The study coordinator or research assistant will respond to any questions about the study procedures at this time. If the patient has any further questions about the procedure or other medical aspects of the study, these will be directed to the surgeon, who will return to complete the consent process once the study coordinator has determined the patient's intent to participate. This will both ensure that all medical questions are directed to a surgeon with accurate knowledge of the relevant procedures as well as insulate the participant from undue influence of deference to a physician.

If patients wish to take more time to think about their participation before making a decision, the study coordinator or research assistant will ask the patient whether the study coordinator or research assistant may follow up by phone within 14 days. If so, the study team member will ask for the best phone number by which to contact the patient for follow up. The study coordinator will then schedule a time for the patient to return to the clinic to complete the consent process if the patient decides to participate.

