If returning to the clinic for an additional consent visit would be too burdensome for the patient – many eligible patients drive or fly several hours to attend appointments at UCLA – the study coordinator will arrange for the patient to complete consent by mail. To do so, the study coordinator will give the patient two copies of the consent form, the HIPAA form, the patient bill of rights, and a pre-paid envelope for returning signed documents. The envelope will be addressed to [name] and delivered to his locked office. The study coordinator will follow up with the patient within approximately 2 weeks to determine whether the patient has made a decision on whether to participate and again probe for further questions, which will be answered by the study coordinator or forwarded to a study surgeon depending on the content. Once the patient has made a decision, the study coordinator will schedule an appointment for the patient to speak with a study surgeon to confirm all questions have been answered and to complete the consent process. The patient may then place the signed consent and HIPAA forms in the pre-paid envelope to mail to the study team. Once the forms are received, the study coordinator will enroll the patient and send the baseline survey as usual. Regardless of methodology, the consent

process will be documented, including date and time of consent, via paper forms which will be stored with the consent form and signed by the physician obtaining consent.

Patients will be recruited until our goal sample size of 50 patients in each arm of the study is achieved. At that time statistical analysis will be performed. Any major complications will be reviewed to determine if the study should be continued.

Privacy and confidentiality:

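### Arms are assigned at scheduling, an unstated interval before the block, which allows avoidable and possibly arm-related loss after randomization and leaves the 50 per arm undefined

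*Combined protocol and SAP*

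**What the plan says.** **Time of assignment.** Under Study design/methodology: "When surgery is scheduled, each enrolled patient will be randomized". The method is described as "alternating, blocked randomization", and "Randomization will maintain equal numbers of participants in each group by sex". The same section places the TQL block, or the control group's needle through the skin, after induction. The time from scheduling to surgery is not stated.

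**What can change in between.** Under Background and Significance, donors have "the option of changing their mind until the day of kidney donation". Under Informed Consent Process, the study is introduced after the surgical consultation and "tentative approval for kidney donation by the living donor team". Study Population lists the exclusions: "Pregnant patients will be excluded" and "Patients with local infection at the potential block site or any contraindication to kidney donation, local, or general anesthesia will be excluded". No time is given for checking or re-checking them. That section also defines the population as patients having the operation.

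**Who is blinded.** Study design/methodology calls the trial single-blinded and says only that patients will not know their treatment.

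**What is counted and analysed.** At the end of Informed Consent Process: "Patients will be recruited until our goal sample size of 50 patients in each arm of the study is achieved". The Statistical Analysis Plan section names t-tests. It gives no analysis population, no replacement rule, and no rule for patients randomized but not operated on or later found ineligible.

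**The concern.** Every day between assignment and the block is a day on which a randomized patient can leave the trial before any outcome exists. Neither the block nor the sham needs the assignment until induction, so this exposure is avoidable.

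Two things are at stake. The first is bias. If someone who knows or can guess the arm decides whether a late problem excludes a patient, the patients left in each arm need no longer be comparable, and a larger sample does not repair that. The second is the denominator. Without a statement of what the 50 counts, the recruitment target, the analysed groups and the balance by sex may refer to different sets of patients. Balance by sex is achieved among randomized patients and need not carry over to those operated on.

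**Working it through.** **1. Sequence of events, from the protocol.**

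| Step | Stated timing |
|---|---|
| Study introduced and consent sought | After surgical consultation and tentative donor approval |
| Arm assigned | When the operation is scheduled |
| Donor may still withdraw | Up to the day of donation |
| Exclusions checked or re-checked | Not stated |
| Block or sham needle | After induction |
| First pain score | Recovery unit onward |

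Loss can therefore fall between the second and fifth steps, and any such patient who is not operated on has no pain score.

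**2. Could the loss relate to arm?** Withdrawal by a donor who does not know the arm should not. A judgement by staff could, because no staff member is stated to be blinded and an alternating sequence can be predicted. The procedures also differ: the study arm receives an ultrasound-guided injection beneath the muscle fascia, while controls receive a needle just through the skin at the same place. The documents do not say that an infection there would be weighed differently by arm. They also do nothing to prevent it.

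**3. The plan's own sample size.** Inputs from the last row of Table 1: means 7 and 5 (difference 2), SD 3, power 80%, n = 37 per group. Alpha is not stated; two-sided 0.05 is assumed.

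- Normal approximation: n = 2 × (1.960 + 0.842)² × 3² / 2² = 2 × 7.85 × 2.25 = 35.3, rounded up to 36.
- Two-sample t-test (noncentral t): power is 79.7% at 36 and 80.8% at 37, so n = 37, as stated. The same method reproduces all nine rows of Table 1.

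**4. Room for loss.** 50 − 37 = 13 per arm, and 13 / 50 = 26%.

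**5. Effect of loss on power.** The documents give no cancellation rate. Assume 5-15% of scheduled donors yield no outcome:

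- Lost per arm: 50 × 0.05 = 2.5 to 50 × 0.15 = 7.5.
- Remaining per arm: 47.5 down to 42.5.
- Share of the margin used: 2.5 / 13 = 19% to 7.5 / 13 = 58%.

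Power for a difference of 2 and SD 3 (t-test, two-sided 0.05):

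| n per arm | Power |
|---|---|
| 50 | 91.0% |
| 48 | 89.8% |
| 45 | 87.9% |
| 42 | 85.5% |
| 40 | 83.8% |
| 37 | 80.8% |

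If 10% are lost in one arm only (50 against 45), power is 89.4%. For a 40% reduction (7.5 against 4.5, SD 3), power at 37 per arm is still 98.9%.

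**6. Scale of a possible bias (illustration).** Suppose a fraction f of one arm is removed because of the arm, and those patients would have scored g points away from the patients who remain. That arm's mean then shifts by f × g. With f = 5-15% as above and g assumed to be 1-3 points, the shift runs from 0.05 × 1 = 0.05 to 0.15 × 3 = 0.45 points. Against a difference of 2 points this is 2.5% to 22.5%. The upper end requires all of the assumed loss to be arm-related and confined to one arm, so it is a bound under these assumptions, not an expectation.

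**The case against.** The strongest case on the other side is that this is mainly a gap in the description. Donors are carefully screened, including by CT, before the study is raised with them. Assignment already waits from enrolment until scheduling, so some early attrition precedes it. The best-documented route of loss is a donor's change of mind, and donors are blinded. A new contraindication to donation or general anesthesia stops surgery in either arm. The infection criterion is worded without regard to arm. The Statistical Analysis Plan section chose 50 precisely because some patients may not complete.

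Much of this stands, and it rules out several stronger readings that a reader might infer:

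- *That eligibility cannot be confirmed before assignment.* It can be checked at scheduling. The difficulty is that the check can become out of date.
- *That the plan builds in post-randomization exclusions, or exclusions that differ by arm.* It is silent on them. Arm-related exclusion is a risk left open, not a stated feature.
- *That excluded patients count towards the 50.* This is plausible, since a patient has an arm only once randomized, but the text does not say so.
- *That power is in danger.* Under the assumed losses it is not.
- *That patients wait 2-3 months between assignment and surgery.* As worded in Study Duration/Study Timeline, that interval runs from consent for surgery to scheduling, which is before assignment.

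What the objection does not answer is why the arm should be fixed at scheduling when nothing before induction depends on it. Nor does it say what protects late eligibility decisions from knowledge of the arm. The documents do not state who holds the allocation or when it is disclosed.

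**Conclusion.** The concern holds in a limited form. Assigning the arm at scheduling permits loss after randomization that later assignment would largely avoid. Because only patients are stated to be blinded and the sequence is alternating, some of that loss could be related to arm. The plan also leaves open what the 50 per arm counts and who is analysed.

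The consequence is possible bias and an unclear denominator. Power is not the issue: an assumed 5-15% loss leaves 42.5-47.5 per arm, and at the whole numbers just outside that range (42 and 48) power is 85.5% and 89.8%. Loss would have to exceed 26% per arm before fewer than 37 remained. The size of any bias cannot be read from the documents, which give neither a cancellation rate nor the interval from assignment to surgery. The illustrative range of 0.05-0.45 points rests wholly on assumptions. This is a worthwhile and cheap improvement, not a flaw that invalidates the trial.

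**What to change.** In Study design/methodology, replace assignment at scheduling with release of the assignment on the day of surgery, after two documented steps: a re-check of the Study Population criteria and confirmation that the donor will proceed. Keep the blocks by sex.

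In the recruitment and Statistical Analysis Plan text, state that:

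- the 50 per arm are counted from patients randomized at that point;
- all of them are analysed in their assigned arm;
- any later exclusion is reported by arm, with its reason.

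The cost is a short wording change and one practical burden: the ultrasound block set-up and the study drug, which the protocol describes as expensive, must be ready for every enrolled case until the assignment is released. Because controls already receive a sham needle at the same site, the sequence of procedures does not change.

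If release on the day proves unworkable, a weaker alternative is to keep the present timing, have late eligibility decided by someone blind to arm, and still define the denominator and analysis population as above.
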